#### 8.2.2 Exclusion Criteria

A participant will be excluded from the study if he or she meets any of the following criteria:

1. Participant has mild, moderate, or critical COVID-19 defined in accordance with the FDA Guidance for Industry:

- a. Mild COVID-19:
  - i. Symptoms of mild illness with COVID-19 that could include fever, cough, sore throat, malaise, headache, muscle pain, gastrointestinal symptoms, without shortness of breath or dyspnea
  - ii. No clinical signs indicative of moderate, severe, or critical severity
- b. Moderate COVID-19:
  - i. Symptoms of moderate illness with COVID-19, which could include any symptom of mild illness (fever, cough, sore throat, malaise, headache, muscle pain, gastrointestinal symptoms) or shortness of breath with exertion
  - ii. Clinical signs suggestive of moderate illness with COVID-19, such as respiratory rate  $\geq 20$  breaths per minute, peripheral oxygen saturation ( $\text{SpO}_2$ )  $> 93\%$  on room air at sea level, heart rate  $\geq 90$  beats per minute
  - iii. No clinical signs indicative of severe or critical illness
- c. Critical COVID-19:
  - i. Respiratory failure defined based on resource utilization requiring at least one of the following:
    - Endotracheal intubation and mechanical ventilation
    - Oxygen delivered by high-flow nasal cannula ([HFNC] heated, humidified, oxygen delivered via reinforced nasal cannula at flow rates  $> 20$  L/min with fraction of delivered oxygen  $\geq 0.5$ )
    - Noninvasive positive pressure ventilation
    - ECMO, or
    - Clinical diagnosis of respiratory failure (i.e., clinical need for one of the preceding therapies, but preceding therapies not able to be administered in setting of resource limitation)
  - ii. Shock (defined by systolic blood pressure  $< 90$  mmHg, or diastolic blood pressure  $< 60$  mmHg or requiring vasopressors)
  - iii. Multi-organ dysfunction/failure

2. Participant has taken investigational medications within 7 days or 5 half-lives prior to enrollment, whichever is shorter.
3. Participant has required any new form of sedation, anxiolysis or central nervous system (CNS) depressant within the 48 hours prior to enrollment that would interfere with neurologic assessments at enrollment.
4. Has history of cerebrovascular accident or intracranial bleeding of any kind, acute coronary syndrome, myocardial infarction, or severe pulmonary hypertension.

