5. Participant has chronic respiratory failure not associated with COVID-19, defined as prior need for home oxygen, need for home noninvasive positive-pressure ventilation (NIPPV) for reasons other than isolated sleep apnea, or other signs of chronic respiratory failure, in the investigator's judgment.
6. Upper gastrointestinal (GI) bleed evidenced by hematemesis, "coffee-ground" emesis or nasogastric aspirate, or hematochezia thought to originate from upper GI tract.

7. Participant has abnormal liver function defined as any 2 of the following at screening:
  - a. Total bilirubin  $\geq 2 \times$  ULN
  - b. Alanine aminotransferase (ALT)  $\geq 3 \times$  ULN
  - c. Aspartate aminotransferase (AST)  $\geq 3 \times$  ULN
  - d. Alkaline phosphatase (ALP)  $> 3 \times$  ULN
  - e. Gamma-glutamyl transferase (GGT)  $> 3 \times$  ULN
8. Participant has an estimated glomerular filtration rate (eGFR)  $< 60$  mL/min.
9. Participant has a known allergy or significant adverse reaction to varespladib-methyl or related compounds.
10. Participant is considered by the investigator to be unable to comply with protocol requirements due to geographic considerations, psychiatric disorders, or other compliance concerns; or has any serious medical condition or clinically significant laboratory, ECG, vital sign, or physical examination abnormality that would prevent study participation or place the participant at significant risk, as judged by the Investigator.
11. Participant is breast-feeding, pregnant, has a positive serum hCG pregnancy test, or is not willing to use a highly effective method of contraception for 14 days after treatment.  
Highly effective methods of contraception are as follows:
  - a. Combined (estrogen- and progestogen-containing) hormonal contraception associated with inhibition of ovulation (oral, intravaginal, or transdermal)
  - b. Progestogen-only hormonal contraception associated with inhibition of ovulation (oral, injectable, or implantable)
  - c. Intrauterine device, intrauterine hormone-releasing system
  - d. Bilateral tubal occlusion
  - e. Vasectomized partner
  - f. Sexual abstinence
  - g. Double-barrier method (condoms, sponge, diaphragm, with spermicidal jellies, or cream)

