6.1.7. Derived Variables

- Respiratory failure is defined as the requirement for use of intubation/mechanical ventilation, an oxygen rate with high flow nasal cannula greater than 20 L/min, non-invasive positive pressure respiratory support, or ECMO, or clinical diagnosis of respiratory failure.
- Respiratory failure-free survival is defined as the combination of no respiratory failure (defined above) and no report of mortality from any cause.
- Mortality from any cause is defined as death listed on the Study Completion CRF or WHO 9-point ordinal scale assessment of death.
- Non-invasive positive pressure respiratory support is defined as the use of continuous positive airway pressure (CPAP) or bilevel positive airway pressure (BiPAP).
- Ventilator use is defined as the use of mechanical ventilation, CPAP, or BiPAP.
- Organ failure is defined as a reported AE indicating a ‘failure’ of respiratory, cardiovascular, hepatic, renal, coagulation, or neurological reported at the PT level or

‘insufficiency’ reported as the lowest level term.

- Renal stabilization or replacement is defined as reported use of any type of dialysis in concomitant medications with a route recorded as (“HEMODIALYSIS”, “PERITONEAL DIALYSIS”, or “DIALYSIS”).
- Time to initiation of supplemental oxygen or other respiratory support in the first 28 days after randomization = (the earliest of Day 28 or date/time of the first use – date/time of randomization) + 1.
- Duration of supplemental oxygen or other respiratory support in the first 28 days after randomization = (the earliest of Day 28 of the study or date/time of the last use – the latest of date/time of the first supplemental oxygen or other respiratory support or date/time of randomization) + 1.
- Time to initiation of intubation/mechanical ventilation, an oxygen rate with high flow nasal cannula greater than 20 L/min, non-invasive positive pressure respiratory support, ECMO in the first 28 days after randomization = (the earliest of Day 28 or date/time of the first support – date/time of randomization) + 1.
- Duration of intubation/mechanical ventilation, an oxygen rate with high flow nasal cannula greater than 20 L/min, non-invasive positive pressure respiratory support, or ECMO in the first 28 days after randomization = (the earliest of Day 28 of the study or date/time of the last specified respiratory support – the latest of date/time of the first specified respiratory support or randomization) + 1.

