8.2.7. Ventilator-Free Days

The number of ventilator-free days from randomization through Day 28 will be summarized descriptively and analyzed using ANCOVA. The LS means will be presented along with the associated 95% CI within each treatment group. In comparing treatments, LS mean differences between treatments will be presented along with associated 95% CIs and p-values. In order to assign the worst total score for death, participants that die will have all days from randomization through day 28 treated as if they had been on a ventilator.

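### SAP 6.1.7 counts any CPAP or BiPAP as ventilator use and as positive-pressure support, though exclusion 5 spares home users with isolated sleep apnea: ventilator-free days are lost, and the primary endpoint is at risk

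*SAP*

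**What the plan says.** **Entry.** Protocol 8.2.2, exclusion 5, removes patients with chronic respiratory failure, one marker of which is "need for home noninvasive positive-pressure ventilation (NIPPV) for reasons other than isolated sleep apnea". Home users with isolated sleep apnea are therefore not excluded on that ground. Exclusion 1.c.i removes critical COVID-19: "Respiratory failure defined based on resource utilization requiring at least one of the following". Its list includes noninvasive positive pressure ventilation and has no sleep-apnea exception.

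**Outcome.** Protocol 13.1.4.1 defines the primary endpoint by pointing back to exclusion 1.c.i. SAP 6.1.7 restates it: "Respiratory failure is defined as the requirement for use of intubation/mechanical ventilation", and among the other qualifying supports "non-invasive positive pressure respiratory support, or ECMO, or clinical diagnosis of respiratory failure". The positive-pressure component is then defined on its own line: "Non-invasive positive pressure respiratory support is defined as the use of continuous positive airway pressure (CPAP) or bilevel positive airway pressure (BiPAP"). Success on the primary endpoint follows: "Respiratory failure-free survival is defined as the combination of no respiratory failure (defined above) and no report of mortality from any cause".

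**Ventilator-free days.** SAP 6.1.7 says: "Ventilator use is defined as the use of mechanical ventilation, CPAP, or BiPAP". SAP 8.2.7 says: "The number of ventilator-free days from randomization through Day 28 will be summarized descriptively and analyzed using ANCOVA", and treats every day through Day 28 as a ventilator day for anyone who dies.

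Neither document takes a habitual or pre-existing device out of any of these definitions.

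**The concern.** Protocol 7.2 explains that the entry limits are there so that progression of acute respiratory failure can be measured more clearly. A device worn at night for sleep apnea before COVID-19 is not progression and has nothing to do with varespladib. If it is counted, the endpoint partly records a background condition. That dilutes any real difference, and a chance excess of such participants in one arm can create or hide one.

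The arms are small. SAP section 10 now has Part 1 (N=18) reported with summary statistics and confidence intervals for primary and secondary outcomes, so a single participant is visible in the percentages.

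**Working it through.** There is no stated figure to reproduce: SAP 3.2 says the sample size has no formal power calculation, and neither document gives an event rate. The check is a side-by-side reading, followed by arithmetic on labelled assumptions.

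**1. Ventilator-free days.** The ventilator-use definition rests on use alone and has no requirement wording. Assume that one night of use makes a ventilator day, since SAP 8.2.7 does not say how a day is counted.

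- Nightly user, alive and otherwise well: 28 − 28 = 0 ventilator-free days.
- Participant who dies: all 28 days treated as ventilator days, so 28 − 28 = 0.
- Largest shift in an arm mean from one such participant who would otherwise have 28: 28/3 = 9.3 days, 28/5 = 5.6 days, 28/36 = 0.8 days.

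**2. Respiratory failure.** The result depends on how the text is read at entry and at outcome.

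| Entry reading of exclusion 1.c.i | Outcome reading | Result for a home user |
|---|---|---|
| Any positive-pressure use | Either | Excluded if using the device at screening. A user who is off it then and resumes later may still enrol |
| Need arising from COVID-19 | Same need-based reading | Enrolled; device not counted |
| Need arising from COVID-19 | SAP component line taken literally | Enrolled; counted as respiratory failure |

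In the last row, nightly use is present both during the 28 days and on Day 28, so the participant fails whether the endpoint is read as ever or at Day 28. The same coding carries into SAP 8.2.3. In SAP 8.2.5, duration runs from the later of first support or randomization to last use, capped at Day 28. It can therefore reach about 28 days, again the value assigned to death.

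**3. Weight of one participant.** Formula: 100/n points. Arm sizes come from SAP 3.2 (5:5:5:3; 72 randomized 1:1, so 36 per arm).

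- 100/5 = 20 points
- 100/3 = 33.3 points
- 100/36 = 2.8 points

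**4. How many would be reclassified.** Assumptions not in the documents: a share s of 5-15% are home users, all keep using the device, all are coded literally, and a fraction f = 30% would fail anyway. Only s(1 − f) of participants then change status.

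| s | Users per arm, 36s | Reclassified per arm, 36s(0.70) | P(at least one in Part 1), 1 − (1 − 0.70s)^18 |
|---|---|---|---|
| 5% | 1.8 | 1.26 | 1 − 0.965^18 = 47% |
| 10% | 3.6 | 2.52 | 1 − 0.930^18 = 73% |
| 15% | 5.4 | 3.78 | 1 − 0.895^18 = 86% |

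**5. Average dilution.** If a share s fails by definition in both arms, the true difference is multiplied by (1 − s). For assumed failure rates of 30% v 15%, 15 points become 15 × 0.95 = 14.25, 15 × 0.90 = 13.5 and 15 × 0.85 = 12.75.

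**The case against.** A reader might infer that every sleep-apnea user is automatically a primary-endpoint failure. The documents do not force that.

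- **Requirement wording.** The SAP's parent definition speaks of a requirement for use. Protocol 7.1, exclusion 1.c.i and SAP 8.2.3 all use requiring. The CPAP/BiPAP line can be read as only naming the devices that make up one component. On that reading, habitual use in someone breathing room air by day is not respiratory failure. This stands, and it is why the primary-endpoint effect is a risk only. It does not settle the matter: the component is defined by use, a sleep-apnea patient can be said to require the device, and no rule tells the programmer which reading governs.
- **Entry.** Automatic failure needs exclusion 1.c.i to be read by purpose at entry and literally at outcome. Read literally at both, users on the device at screening never enrol, but the exception in exclusion 5 then has little effect. This also stands as a limit. It shows that the passages do not fit together.
- **Data source.** Protocol 10.3.1.1 bases ventilation endpoints on the investigator's assessment of need for oxygen support. Concomitant therapies are also recorded through Day 28 (Protocol 9.9 and Table 2-1), but no text says the respiratory-failure flag is derived from them. Whether a home device reaches the endpoint depends on case report forms not shown here. This reservation applies to ventilator-free days too.
- **Stakes.** The trial is exploratory, Part 1 efficacy has no hypothesis tests or p-values, and Part 2 had one participant at the pause. This lowers the severity. It does not protect small-arm percentages and means from one recoded participant.

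**Conclusion.** The gap is real and should be fixed; it is not a critical fault. It is firmest for ventilator-free days, where the definition rests on use alone and a nightly home user who is enrolled and recorded scores about the same as a participant who died. For the primary endpoint and SAP 8.2.3 and 8.2.5, misclassification is one plausible reading.

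The number affected is unknown. One reclassified participant is worth 20 or 33 points in a Part 1 arm and 2.8 points in a planned Part 2 arm. The estimates of about 1.3-3.8 per Part 2 arm and a 47-86% chance of at least one in Part 1 rest wholly on the assumed 5-15% share, continued use, literal coding and a 30% underlying failure rate. Average dilution is modest, about 0.8 to 2.3 points off an assumed 15. Chance imbalance in small arms matters more.

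**What to change.** Before database lock, amend SAP 6.1.7 so that CPAP or BiPAP counts as respiratory failure and as ventilator use only when, for acute respiratory failure, it is either newly started after randomization or extended beyond the participant's pre-enrolment sleep-apnea use. Continuing or resuming a device documented in medical history for isolated sleep apnea should not count. Apply the rule to the primary endpoint and to SAP 8.2.3, 8.2.5 and 8.2.7.

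Identify affected participants blind to treatment from medical history, concomitant-therapy and oxygen-support records. The rule should not rely on device settings, which the documents do not say are collected. Show the primary endpoint and ventilator-free days under both rules.

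Separately, the sponsor should reconcile exclusion 1.c.i with exclusion 5, so that sites and the analysis treat these patients alike. SAP section 10 already announces a protocol and SAP amendment for Part 2, which could carry this change.

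The cost is a short definition, one blinded record review and a second display. The downside is a small blinded judgement, for a few participants, on whether use went beyond the habitual pattern.

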### **9.5. Discontinuation of Study Intervention**

#### **9.5.1 Individual Participant Halting Criteria**

If a clinically significant finding is identified (including, but not limited to, deterioration from baseline) after enrollment, the investigator or qualified designee will determine if any change in participant management is needed. Every effort should be made to administer the planned doses. Dosing should be held for a participant who experiences any of the following toxicities:

- Any Grade  $\geq 2$  creatinine increase ( $> 1.5 \times$  baseline or ULN)
- Any new, treatment-emergent occurrence of any of the following adverse events of special interest:

- Cerebrovascular accident
- Acute coronary syndrome
- Supraventricular arrhythmia requiring urgent medical intervention
- Any ventricular tachycardia/fibrillation including Torsade de Pointes
- Hepatic toxicity with AST and/or ALT  $\geq 3 \times$  ULN for 2 days or  $> 5 \times$  ULN on one occasion

If a participant becomes unable to swallow the IP due to worsening of their condition, nasogastric administration or a dose delay may be considered in consultation with the medical monitor. In general, treatment with IP should continue for the full 7 days unless the participant is unable to continue treatment or if it is the participant's best interest to discontinue treatment. If a participant must discontinue IP, every effort will be made to continue the participant in the study through Day 60. If a participant experiences an SAE judged to be related to the IP, the treatment for that participant will be permanently discontinued from the IP, but every effort will be made to continue the participant in the study through Day 60.

Any new clinically relevant adverse finding will be reported as an adverse event (AE) as defined in [Section 11.1](#).

Discontinuation from IP does not mean discontinuation from the study, and remaining study procedures should be completed as indicated by the study protocol.

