### **9.5.2 Management of Acute Kidney or Liver Injury**

Acute kidney/liver injury has been reported as a possible complication during the disease progression of COVID-19.

Extra caution and monitoring will be exercised when treating patients with COVID-19-induced hepatic dysfunction. Given the relatively short duration of treatment (7 days) compared to previous studies with varespladib and the transient nature of hepatic enzyme elevation, subjects with acute liver injury will continue IP and be closely monitored with clinic visits and repeated blood work including liver function tests on Days 14 and 28. If hepatic enzymes exceed the hepatic toxicity limits specified in [Section 9.5.1](#), IP should be discontinued. However, every effort will be made to continue the participant in the study through Day 60.

In the event of acute kidney injury secondary to COVID-19, the subsequent dose of the study drug will be withheld and will be recommenced once renal parameters become normal and an interval of at least 5 hours is available before the next dose. Once recommenced, IP will be given through the original 7-day treatment period and the missed dose will not be taken. If renal function is persistently abnormal and the participant misses study drug more than 24 hours, their IP treatment should be discontinued.

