#### **10.3.3.1.2 Evaluation of Clinical Laboratory Values**

Each local laboratory will provide the normal ranges of values for the clinical laboratory assessments in this study, and the local ranges will be regarded as the reference ranges on which decisions will be made by each investigator.

If a laboratory value is out of the reference range, it is not necessarily clinically relevant. The investigator must evaluate the out-of-range values and record his or her assessment of the clinical relevance in the appropriate eCRF.

All clinical laboratory values that in the investigator's opinion show clinically relevant or pathological changes during or after termination of treatment must be reported as AEs and followed, as described in [Section 11.2](#).

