## 11. ADVERSE EVENTS

### 11.1. Definitions

#### 11.1.1 Adverse Events

An AE is defined as any untoward medical occurrence in a patient or clinical investigation participant administered an investigational product that does not necessarily have a causal relationship with this treatment. An AE can therefore be any unfavorable and unintended sign (including an abnormal laboratory finding, physical examination finding, or neurological finding), symptom, or disease temporally associated with the use of a medicinal product, whether or not related to the medicinal product.

Pre-existing diseases or conditions will not be considered AEs unless there is an increase in the frequency or severity or a change in the quality of the disease or condition. Worsening of a pre-existing condition is considered an AE. Worsening or progression of the COVID-19 disease under study will not automatically be considered an AE unless the investigator believes that the progression is related to study drug. In that case, the worsening or progression of COVID-19 disease under study will be reported as an AE / SAE as appropriate.

Events that occur in participants treated with placebo, or during treatment-free periods of the study, are also considered AEs.

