### **11.2. Event Assessment and Follow-up of Adverse Events**

The occurrence of an AE or SAE may come to the attention of study personnel during hospitalization and at outpatient visits or via telephone.

All AEs will be captured on the appropriate case report form (CRF). Information to be collected includes event description, time of onset, clinician's assessment of severity, relationship to IP (assessed only by those with the training and authority to make a diagnosis), and time of resolution/stabilization of the event. All AEs occurring while on study must be documented appropriately regardless of relationship. All AEs will be followed to adequate resolution.

Site staff will record all reportable events with start dates occurring any time after informed consent is obtained through Day 60. At each study visit, the investigator will inquire about the occurrence of AE/SAEs since the last visit. Events will be followed for outcome information until resolution or stabilization.

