#### **11.2.1 Assessment**

The investigator is responsible for the detection and documentation of events meeting the criteria and definition of an AE or SAE described previously. During hospitalization and at each outpatient visit or telephone visit, the participant will be allowed time to spontaneously report any issues since the last visit or evaluation. The investigator will then monitor and/or ask about or evaluate AEs using nonleading questions, such as

- “How are you feeling?”
- “Have you experienced any issues since your last visit?”
- “Have you taken any new medications since your last visit?”

Any clinically relevant observations made during the visit will also be considered AEs.

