8.2.9. Organ Failure-Free Days

The number of organ failure-free days from randomization through Day 28 will be summarized descriptively and analyzed using ANCOVA. The LS means will be presented along with the associated 95% CI within each treatment group. In comparing treatments, LS mean differences between treatments will be presented along with associated 95% CIs and p-values. In order to assign the worst total score for death, participants that die will have all days from randomization through day 28 treated as if they had organ failure.

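### Organ failure in survivors is counted only from reported AEs, which COVID-19 progression need not generate, so ventilated or dialysed survivors can score 28 organ failure-free days

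*SAP*

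**What the plan says.** SAP 6.1.7 (Derived Variables): "Organ failure is defined as a reported AE indicating a" failure of the respiratory, cardiovascular, hepatic, renal, coagulation or neurological system at preferred-term level, or an insufficiency at lowest-level-term level. No other source is named.

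SAP 8.2.9 (Organ Failure-Free Days) makes one exception: "participants that die will have all days from randomization through day 28 treated as if they had organ failure". Deaths therefore do not depend on AE reporting.

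Protocol 11.1.1 (Adverse Events): worsening or progression of the disease under study "will not automatically be considered an AE unless the investigator believes that the progression is related to study drug". Its next sentence ties reporting as an AE or SAE to that belief.

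Protocol 9.5.2: "Acute kidney/liver injury has been reported as a possible complication during the disease progression of COVID-19". Protocol 5.1 names respiratory failure and multiorgan failure among the complications of critical disease.

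Several passages push reporting up:
- Protocol 9.5.1: "Any new clinically relevant adverse finding will be reported as an adverse event (AE) as defined in" Section 11.1.
- Protocol 10.3.3.1.2, on laboratory results which, in the judgement of the investigator, "show clinically relevant or pathological changes during or after termination of treatment must be reported as AEs and followed".
- Protocol 11.2: "All AEs occurring while on study must be documented appropriately regardless of relationship".
- Protocol 11.2.1: "Any clinically relevant observations made during the visit will also be considered AEs".
- Protocol 11.2.2.5 and 11.3.1 have the investigator weigh COVID-19 as an explanation when judging relationship to study drug, which presupposes that the event has been recorded.

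**The concern.** Organ failure caused by COVID-19 is what the drug is meant to prevent, and it is also the kind of event that Protocol 11.1.1 allows to go unfiled as an AE. Where that happens in a survivor, SAP 6.1.7 scores those days as failure-free.

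The same section derives ventilator use from use of the device and dialysis from the concomitant-medication data, neither through an AE. The WHO scale records intubation (score 6) and ventilation plus additional organ support (score 7). The organ-failure endpoint can therefore contradict the trial's other data on the same participant.

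Protocol section 6 lists three endpoints under the morbidity and mortality objective: mortality, days without renal replacement, and organ failure-free days. The last is the only broad non-fatal morbidity measure of the three. SAP 10 now plans summary statistics and confidence intervals for the secondary outcomes in the 18 Part 1 participants.

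**Working it through.** The documents give no figure on this point and the sample size has no power basis, so there is nothing to reproduce. The check is a comparison of texts followed by illustrative arithmetic.

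**1. Does any passage close the gap?**
- Protocol 9.5.1 refers back to the AE definitions in 11.1, which contain the progression rule.
- Protocol 11.2 requires documentation of events that already are AEs.
- Protocol 10.3.3.1.2 and 11.2.1 carry no such limit. They pull against 11.1.1 but do not cancel it.
- The missing-data rule in SAP 6.1.4 does not clearly reach the case. An event never filed as an AE is not a missing value under 6.1.7; the participant simply scores 28.
- A filed AE may still not count. The protocol's own phrases acute kidney injury and acute respiratory distress syndrome contain neither failure nor insufficiency, so the result depends on coding and on how the definition is read.

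Capture is therefore partial, and its level is unknown.

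**2. One participant.** A survivor is ventilated for 14 days with no qualifying AE.
- Ventilator-free days: 28 − 14 = 14.
- Organ failure-free days: 28 − 0 = 28.

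**3. One arm mean.** Arm sizes follow from SAP 3.2: 5, 5, 5 and 3 in Part 1, and 72/2 = 36 per arm in Part 2. Episode length d is an assumption of 7 to 14 days. One unrecorded episode raises its arm mean by d/n.

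| Arm | n | d = 7 | d = 14 |
|---|---|---|---|
| Part 1, each active arm | 5 | 7/5 = 1.4 | 14/5 = 2.8 |
| Part 1, placebo | 3 | 7/3 = 2.3 | 14/3 = 4.7 |
| Part 2, if completed | 36 | 7/36 = 0.19 | 14/36 = 0.39 |

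**4. Allowing for frequency.** Mean overstatement among survivors = p × D × u, where p is the share with organ failure, D the mean days of failure and u the share not recorded. All three are assumptions. With p = 10–30%, D = 5–10 days and u = 0–100%, the range is 0 to 0.30 × 10 × 1 = 3.0 days. For example, 0.20 × 10 × 0.50 = 1.0 day.

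**5. Direction.** If the captured fraction c is the same in both arms and unrelated to duration, the non-fatal part of a treatment difference is multiplied by c in expectation. An assumed c of 0.5 to 0.9 loses 50% to 10% of it. If the unrecorded share differs by arm, say 50% against 25% with p = 30%, D = 10 and no true effect, a spurious difference of 0.30 × 10 × 0.25 = 0.75 days appears.

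**6. Against sampling error.** The documents give no SD. At an assumed SD of 5–10 days, the t-based 95% half-width is about 6–12 days at n = 5 (2.776 × SD/√5) and about 12–25 days at n = 3 (4.303 × SD/√3). Both exceed the shifts in step 3.

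**The case against.** The best case against the point is that under-capture is inferred, not shown. Protocol 10.3.3.1.2 is unconditional once the investigator judges a laboratory change relevant. Section 11.2.1 makes clinically relevant observations AEs. Section 11.3.1 says that stroke, myocardial infarction and malignant arrhythmias may also come from COVID-19 and still treats them as AEs. Together these suggest that the protocol separates recording an event from attributing it. Whether a newly diagnosed organ failure is progression of COVID-19 or a new event is also a matter of reading, and Protocol 9.5.2 speaks of injury, not failure. All of this stands as a reason to expect partial capture, possibly complete. It does not remove the rule in 11.1.1 or give the SAP a second source.

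A reader might infer that organ failure in survivors goes largely uncounted, or that the definition favours varespladib. The documents support neither. They leave filing open, and assignment is blinded. An unrecorded episode flatters whichever arm it falls in.

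The size is also rightly questioned. The per-episode shift is conditional on an unrecorded episode occurring, and SAP 10 does not say that an active-minus-placebo contrast will be reported for Part 1. SAP 10 reports only one participant recruited to Part 2 at the pause, so the n = 36 figures apply only if that part is completed. SAP 6.1.8 lists all collected data, so a careful reader could see ventilation and dialysis beside the AEs. These points lower the severity. They do not make the derivation correct.

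**Conclusion.** The point holds as a textual gap. A stated derivation rule can give a result that contradicts the SAP's own ventilator, dialysis and WHO-scale data for the same survivor. Confidence is high on that and low on its effect: the frequency of unrecorded episodes is not in the documents and may be zero. Every figure in days rests on assumed episode lengths, frequencies or capture rates, and in Part 1 the shift is likely smaller than sampling error.

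Severity is minor to moderate. This is one of 13 secondary endpoints, it is not among the key secondaries in SAP 8.1.1, the study is exploratory, and Part 1 has no efficacy tests. A reader might infer that the primary endpoint shares the flaw. It does not, because its respiratory-failure definition does not depend on an AE being reported.

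**What to change.** In SAP 6.1.7, keep any reported organ-failure AE as a source. In addition, count a day as organ failure, whatever the AE status, when the data show any of the following:

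- **Respiratory support** that section 6.1.7 already counts by duration: mechanical ventilation, qualifying high-flow nasal cannula, non-invasive positive pressure support or ECMO. Do not count pre-existing home CPAP or BiPAP for isolated sleep apnea, which exclusion criterion 5 permits. Count clinically diagnosed respiratory failure only where start and stop dates are recorded, since 6.1.7 gives no way to count its days.
- **Dialysis** as defined in 6.1.7.
- **A vasopressor** in the concomitant-medication data, from a code list fixed before unblinding.

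Use WHO scores 6–7, recorded daily to Day 21 and at Day 28, as a cross-check. Keep the death rule of 8.2.9. Keep AE-based capture for hepatic, coagulation and neurological failure, and state in the report that it may be incomplete in survivors.

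Make the change before the Part 1 database lock, or label it post hoc as SAP 1 (Overview) requires. Add it to any Part 2 SAP amendment; the one foreseen in SAP 10 concerns only the endpoints of 8.2.4 and 8.2.5.

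The cost is SAP wording, a code list and some programming. Protocol 9.9 and 10.3.1.1 indicate that the therapy and oxygen-support data are already gathered, but the eCRF is not among the documents and should be checked. AE recording does not change. The downside is more overlap with ventilator-free days and renal-replacement days.

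Separately, the high-flow nasal cannula wording differs: 6.1.7 gives only a flow above 20 L/min, while exclusion criterion 1.c.i adds a delivered oxygen fraction of at least 0.5. Those passages should be reconciled.
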